- pp. All participants will collect solicited signs and symptoms (including body temperature) in an e-Diary via the eCOA from the time of booster vaccination until 7 days after booster vaccination, if feasible. The diary will be reviewed by the study personnel and solicited AEs recorded for a subset of participants ie, participants included in the Safety Subset of the double-blind phase and all participants who received a heterologous prime or booster vaccination outside the study, if feasible. After the signing of informed consent of Amendment 7, no further solicited symptoms will be collected.
- qq. Unsolicited AEs will be recorded for all participants from time of booster vaccination until 28 days after booster vaccination. After signing informed consent of Amendment 7, no further unsolicited symptoms will be collected.
- rr. A ruler to measure local injection site reactions will be distributed to all participants, if feasible.
- ss. To be collected once operationally feasible.

AE = adverse event; AESI = adverse event of special interest; approx.. = approximate; cont. = continuous; COVID-19 = coronavirus disease-2019; d = day(s); eCOA = electronic clinical outcome assessment; eCRF = electronic case report form; ePRO = electronic patient-reported outcome; EUA = Emergency Use Authorization; ICF = informed consent form; MAAE = medically-attended adverse event; MRU = medical resource utilization; SAE = serious adverse event; SARS-CoV-2 = severe acute respiratory syndrome coronavirus-2; SIC = Symptoms of Infection with Coronavirus-19; vac = vaccination; w = week(s).

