To assess the safety and reactogenicity of Ad26.COV2.S at the $5 \times 10^{10}$ vp dose level administered as homologous or heterologous booster vaccination in adults.	
 
Solicited local and systemic AEs for 7 days after booster vaccination.
 
Unsolicited AEs for 28 days after booster vaccination.
 
SAEs and AESIs from booster vaccination until end of the study.
 

To measure the primary endpoints previously utilized for the double-blind portion of the study in this unblinded booster portion of the trial during the time participants have and have not been boosted.	
 
Incidence of the primary endpoints utilized in the double-blind portion of the study, including moderate to severe/critical COVID-19 cases starting at 28 days by serostatus*, in the unblinded booster portion of the study (see definitions of terms in Section 10.1) during the times when they have and have not been boosted.
 

To measure the primary endpoints previously utilized for the double-blind portion of the study in participants infected with selected variants and the reference strain in this unblinded booster portion of the trial during the time participants have and have not been boosted.	
 
Incidence of the primary endpoints (Day 28 after vaccination) in the main study as applicable as described in the first objective but for variants of concern and the reference strain.
 

Secondary Objectives of the Booster Phase	
To evaluate the secondary endpoints previously utilized for the double-blind portion of the study in this unblinded booster portion of the trial during the time participants have and have not been boosted.	
 
Incidence of secondary endpoints (Day 28 after vaccination) from the double-blind portion of the study by serostatus* such as symptomatic severe/critical disease, hospitalization, and death.
 

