- Suspected AESIs (thrombotic events and thrombocytopenia [defined as platelet count below 150,000/ $\mu$ Lb]) will be reported from the moment of vaccination until the end of the study/early

a Vaccination with Ad26.COV2.S may interfere with some serologic assays utilized at local community health clinics/commercial laboratories, by seeking and identifying the spike protein in the vaccine and rendering a false positive result. For this reason, participants will be encouraged to not seek testing outside the study. If a participant requires testing outside of the protocol-mandated testing schedule, the site will guide them on the appropriate assay that identifies the viral nucleocapsid protein (and not the spike protein).

b Updated Proposed Brighton Collaboration process for developing a standard case definition for study of new clinical syndrome X, as applied to Thrombosis with Thrombocytopenia Syndrome (TTS). 18 May 2021. <https://brightoncollaboration.us/wp-content/uploads/2021/05/TTS-Interim-Case-Definition-v10.16.3-May-23-2021.pdf>. Accessed: 02 September 2021.

withdrawal. An AESI Adjudication Committee with appropriate expertise will be established to evaluate each suspected AESI and determine whether it is a case of thrombosis with thrombocytopenia syndrome (TTS). From the time of local approval of protocol Amendment 5 onwards, TTS is considered an adverse event of special interest (AESI).

- All AEs will be followed until resolution or until clinically stable.

As of Amendment 7, for all participants:

- Active follow-up of suspected COVID-19 episodes will be replaced by passive surveillance: during follow-up calls by the site at Month 18 and Month 24, new COVID-19 participant-reported events are to be reported as SAEs, AE or MAAEs.
- Concomitant medications for these events should be reported.
- If a COVID-19 confirmatory laboratory or assay read-out is available, this should be reported in the eCRF (self-reported or as part of CIOMS form).

For participants in the Safety Subset (double-blind phase):

- Solicited AEs, collected through an e-Diary, will be recorded from the time of vaccination until 7 days post-vaccination.
- All other unsolicited AEs, whether serious or non-serious, will be recorded from the time of vaccination until 28 days post-vaccination.

Up to Amendment 7: For participants who received booster vaccination at the Year 1/Booster Visit:

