## Analysis of the Open-label cross-over Phase, Open-label Booster Phase, and Passive Surveillance Phase

Safety, immunogenicity, and efficacy endpoints following cross-over and/or booster vaccination will be descriptively summarized by the different cohorts for the different phases (ie, for the open-label phase: early vaccinated cohort and late vaccinated cohort; ie, for the booster phase: 1-dose cohort, homologous booster cohort and the heterologous booster cohort).

Additional analyses may be conducted to support health authority interactions and/or based on public health demand in case of emerging variants.

If deemed feasible, efficacy of the booster vaccination may be explored by comparing efficacy data after boosting to data in the absence of booster, on the same primary regimen.

Feasibility will be assessed based on data availability as well as adjustments for potential confounding in the statistical analysis.

The following data sources will be explored:

1. If available, data of participants in the study who did not receive a booster and/or available data prior to boosting.
2. Data of individuals outside the study who received a similar primary regimen but did not receive a booster. It will be explored if external data (eg, real world evidence data, and/or published literature data) is available to that end for the countries enrolled in this trial.

For the statistical analysis, it will be explored if adjustment for potential confounding factors is feasible (based on risk factors identified in the analysis of the double-blind phase/and or literature) in each comparison. This may include, but not limit to age, presence of co-morbidities as well as the spatiotemporal evolution of variants and the epidemic. It is anticipated that comparative evaluation of efficacy against asymptomatic infections using real world evidence of data of individuals outside the study will not be feasible due to the difficulty of detecting asymptomatic infections in real world evidence.

Efficacy data may be compared following homologous versus heterologous booster vaccination. Efficacy data after primary vaccination until booster vaccination may be summarized (as immediate, early versus delayed, late vaccination).

Details will be provided in the SAP.

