- z. All (S)AEs related to study procedures or non-investigational sponsor products will be reported from the time a signed and dated ICF is obtained until the end of the study/early withdrawal. All other SAEs are to be reported from the moment of vaccination until completion of the participant's last study-related procedure. AEs leading to study discontinuation (regardless of the causal relationship) are to be reported from the moment of vaccination until completion of the participant's last study-related procedure. Applicable from the time of local approval of protocol Amendment 5 onwards: Suspected AESIs are to be reported from the moment of vaccination until completion of the participant's last study-related procedure (see Section 8.3.1). Special reporting situations, whether serious or non-serious, are to be recorded from the time of each vaccination until 28 days post-vaccination (applicable for both the double-blind and open-label phases of the study). Participants will be reminded once a month to contact the study site in case of an SAE.
- aa. Refer to Section 6.10 for collection and recording of concomitant therapies associated with SAEs, solicited and unsolicited AEs, suspected AESIs, and MAAEs.
- bb. To be collected pre-vaccination only from participants receiving Ad26.COV2.S (after unblinding and/or as booster vaccination at Year 1/Booster Visit) and 28 days post booster vaccination (if applicable). Whole blood samples will be used for a complete blood count, including platelets, in a local laboratory or a substitute for local laboratory, depending on local feasibility towards turnaround time of sample processing. Serum samples will be derived from the whole blood sample and stored for potential future coagulation-related testing in a central laboratory if the participant experiences a suspected AESI (see Section 10.2, Appendix 2).
- cc. Blood sample for humoral immunity at Day 1 (pre-vaccination), Day 29, Day 71, Month 6/Unblinding Visit, Year 1/Booster Visit (pre-vaccination, if applicable), Year 1 + 28 days for participants who received booster vaccination, Year 1 + 72 days for participants who received booster vaccination, and Month 18 (24 weeks after Year 1 Visit), also includes sample for sero-confirmation of SARS-CoV-2 infection.
- dd. Blood samples for immunogenicity will only be taken if the early exit visit is at least 10 days after the previous immunogenicity blood draw.

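### Before Amendment 7 the only platelet count timed after a dose is 28 days post booster, so summaries of suspected AESIs or isolated thrombocytopenia can show a post-booster excess without any vaccine effect

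*Protocol*

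**What the plan says.** **Sampling.** Footnote bb of the pre-Amendment 7 schedule (Section 1.3.3) says of the clinical laboratory sample: "To be collected pre-vaccination only from participants receiving Ad26.COV2.S (after unblinding and/or as booster vaccination at Year 1/Booster Visit) and 28 days post booster vaccination". It adds: "Whole blood samples will be used for a complete blood count, including platelets, in a local laboratory or a substitute for local laboratory". Footnote ss makes the Year 1 and Year 1 + 28 days samples conditional on operational feasibility. In the Amendment 7 schedule for non-subset participants (Section 1.3.1, footnote k) only the pre-booster sample remains, and their outstanding Visits 8 and 9 are cancelled.

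**Event definition.** The Synopsis (Safety Evaluations) lists "Suspected AESIs (thrombotic events and thrombocytopenia [defined as platelet count below 150,000"/µL]. No symptom is required. Footnote z of Section 1.3.3, which applies from local approval of Amendment 5, says: "Suspected AESIs are to be reported from the moment of vaccination until completion of the participant's last study-related procedure". A committee is to "evaluate each suspected AESI and determine whether it is a case of thrombosis with thrombocytopenia syndrome (TTS"), and it is TTS that the protocol names as the AESI. Section 1.3.5 requires a platelet count in any suspected thrombotic event or suspected TTS.

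**Use of the data.** The primary safety endpoint of the booster phase includes "SAEs and AESIs from booster vaccination until end of the study". Safety is to be summarized descriptively by cohort: "for the booster phase: 1-dose cohort, homologous booster cohort and the heterologous booster cohort". Section 4.1 and the Synopsis (Overall Design) add that the booster phase serves to describe safety over boosted and unboosted time. The Synopsis (Safety Analyses) plans no formal test. Section 3.2.2 also lists a platelet endpoint measured on the day of the booster and 28 days later.

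**The concern.** An event that is defined by a laboratory value can be found only where blood is drawn. If one cohort or period has a scheduled draw after its dose and the cohort or period beside it has none, a table will show more events in the first even when the underlying rates are equal.

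Here the event is any platelet count below 150,000/µL. The scheduled post-dose draw follows the booster only, and the neighbouring columns are the 1-dose cohort and unboosted time. TTS is an important identified risk of this vaccine (Section 2.3.1). A difference in low platelets that the visit schedule produced could therefore be read as a safety finding about the booster.

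**Working it through.** **Step 1: where the platelet count is drawn.** Section 1.3.3 states an approximate blood volume range per visit. I rebuilt each range from the schedule rows: humoral sample 10 mL (15 mL in the subsets), RNAseq 2.5 mL, cytokines 5 mL, blood count 7 mL.

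- Day 1 and Day 29: 10 + 2.5 = 12.5 to 15 + 2.5 = 17.5 (stated 12.5 to 17.5)
- Day 71: 10 to 15 (stated 10 to 15)
- Month 6: 10 + 7 = 17 to 15 + 7 = 22 (stated 17 to 22)
- Year 1: 10 to 15 + 7 + 5 + 2.5 = 29.5 (stated 10 to 29.5)
- Year 1 + 1 day: 0 to 5 + 2.5 = 7.5 (stated 0 to 7.5)
- Year 1 + 28 days: 0 to 15 + 7 + 5 + 2.5 = 29.5 (stated 0 to 29.5)
- Year 1 + 72 days: 0 to 15; Month 18: 10 to 15; Year 2: 0 to 15 (all as stated)

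The sums are 72.0 and 183.5 mL, which match the stated cumulative range. All ten ranges reproduce with the 7 mL count at Month 6, Year 1 and Year 1 + 28 days only. By footnote bb the first two are taken before the dose, so Year 1 + 28 days is the one count timed after a dose.

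**Step 2: what that does with no vaccine effect.** The documents give neither of the two quantities needed, so both are assumptions:

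- p, the share of random draws below 150,000/µL: 0.5% to 5%
- d, the share of low counts that would be found clinically without a scheduled draw: 1% to 10%

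With every Day 28 sample taken, the expected rate in boosted participants is p, and in unboosted participants p × d.

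- Boosted: 1,000 × 0.005 = 5 to 1,000 × 0.05 = 50 per 1,000
- Unboosted: 1,000 × 0.005 × 0.01 = 0.05 to 1,000 × 0.05 × 0.10 = 5 per 1,000
- Ratio: p / (p × d) = 1/d, that is 1/0.10 = 10 to 1/0.01 = 100

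If only a share s of boosted participants have the Day 28 sample, the ratio is [s + (1 − s)d]/d = s/d + 1 − s. It runs from 1 at s = 0 to 1/d at s = 1. The documents do not give s.

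**Step 3: the within-person comparison.** One count before and one after the booster have the same expected rate p when there is no effect, so the expected ratio is 1.0. If a low count persists to the second draw with assumed probability r = 0.5 to 0.8, newly low counts at Day 28 number p(1 − r). That is 1,000 × 0.005 × 0.2 = 1 to 1,000 × 0.05 × 0.5 = 25 per 1,000, offset by the same number that return to normal.

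Requiring a new or worse count therefore removes pre-existing low counts, but it does not by itself make boosted and unboosted cohorts comparable. At p = 2%, r = 0.5 and d = 5%, 1,000 × 0.02 × 0.5 = 10 per 1,000 newly low counts still face 1,000 × 0.02 × 0.05 = 1 per 1,000 in unboosted participants.

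**Step 4: assignment to phase.** Under Section 3.2.2 a participant enters the booster phase on the day of the booster visit. The pre-booster sample may be drawn on that same day. Assigned by date alone, a low pre-booster count could be placed in the booster phase.

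**The case against.** Several stronger readings are tempting, and the documents do not support them.

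- *The booster would appear to cause thrombocytopenia.* This does not follow. A pre-booster count exists, the platelet endpoint is paired, and the paired comparison is not inflated (Step 3).
- *Low counts can enter through the schedule only after a booster.* They can also enter before the cross-over dose and before the booster. In participants already primed with Ad26.COV2.S, the pre-booster sample is in effect a late count after the primary dose.
- *The primary AESI endpoint of the booster phase is inflated.* This is not established. The text shown makes TTS the AESI and a low count only a suspected one, to be adjudicated.
- *TTS itself is over-counted, because boosted participants with a thrombosis more often have a platelet count on record.* This is weak. Section 1.3.5 requires a platelet count in any suspected thrombotic event, whether or not the participant was boosted.
- *A fixed number of spurious cases can be given.* A statement such as 100 to 400 per 10,000 boosted participants (10,000 × 1% to 10,000 × 4%) needs a prevalence and a number tested that the documents do not contain.

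It is also fair to say that safety is descriptive, that homologous and heterologous boosted participants share one sampling plan, that table layout commonly belongs to the SAP, and that Sections 8.3.7, 9.7 and 10.4.3 are not in the part at hand. How isolated thrombocytopenia is tabulated could therefore not be checked.

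These points narrow the concern without removing it. The unequal sampling and the side-by-side description are both fixed in the protocol text shown. With no formal test planned, the descriptive tables are what readers will interpret.

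**Conclusion.** The point holds in a limited form. Before Amendment 7 isolated, schedule-found thrombocytopenia is ascertained unequally between cohorts and periods that the protocol itself sets side by side. Descriptive summaries of suspected AESIs or low platelet counts, by cohort or by boosted versus unboosted time, can show an excess after the booster with no vaccine effect. Adjudicated TTS is little affected.

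The size cannot be known from the documents. The 10- to 100-fold ratio rests wholly on the assumed d and on complete Day 28 sampling; conditional sampling and the loss of the Day 28 sample under Amendment 7 pull it toward 1. The Amendment 7 change also makes ascertainment uneven among boosted participants. This is a worthwhile, inexpensive improvement to how the data are summarized. It does not undermine the booster-phase safety assessment as a whole.

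**What to change.** In the protocol's safety analysis text or the SAP:

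1. Flag each thrombocytopenia event as found by scheduled sample or found clinically, and tabulate the two separately.
2. Count a scheduled-sample case as post-booster only if it is new or worse than the participant's own pre-booster count, using the paired platelet endpoint of Section 3.2.2. Show movement in both directions, so that counts returning to normal stand beside newly low ones.
3. Base any comparison between cohorts or doses on clinically detected events and adjudicated TTS.

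The cost is one extra flag, one extra table and fewer events in the cohort comparison. The pre-booster count is already in the schedule. Reporting and adjudication of all suspected AESIs stay as they are.

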### 1.3.4. Participants With (Suspected) COVID-19

#### 1.3.4.1. Passive Follow-up (As of Amendment 7)

As of Amendment 7, active follow-up of suspected COVID-19 episodes will be replaced by a passive follow-up approach.

New suspected COVID-19 episodes will be participant-reported and will not include any laboratory sampling. Site staff will collect information on the new COVID-19 episodes at scheduled time points and report these as SAEs, AEs, or MAAEs, as applicable. Participants may contact the site at any time in between scheduled visits to report COVID-19 episodes. Concomitant therapies related to these events are to be reported, as well as any confirmatory COVID-19 laboratory information, if available.

Guidance on (S)AE coding may be provided.

Some participants will have an ongoing COVID-19 event at time of signing the informed consent of protocol amendment 7. Also, under protocol amendment 7, the eCOA will be decommissioned. Hence participant will stop using the eCOA as of the consent visit. The outstanding activities planned for the follow-up of COVID-19 events will also end on that date for the participants (eg no further samples, no MRU completion, no MA-COV completion, no further visit in the context of the COVID-19 follow-up). The eCOA will be stopped based on approval of protocol Amendment 7 at each study site.

#### 1.3.4.2. Active Follow-up (Prior to Amendment 7)

Timing relative to onset of signs and symptoms	COVID-19 Day 1-2	COVID-19 Day 3-5 a		2-day cycle to be repeated b,c,d,e		COVID-19 Day 29 (±7 d) f,g
		Part 1	Part 2 b	1 st day of cycle	2 nd day of cycle	
Location	Home h	Site or Home i,j	Site or Home i,j	Home j	Home j	Site or Home i,j
Participant to contact study site with any health concerns/participant notifies the site of becoming aware of a positive RT-PCR test	●					
Site to contact participant if COVID-19 signs or symptoms are recorded in eCOA	●					
Confirmation of suspected COVID-19 using prespecified criteria	● k	● l				
Nasal swab sample (collected by the participant at home) m	● n			●		
Nasal swab sample (collected by qualified study staff)		● o				
Saliva sample (collected by the participant) p			●		●	
Humoral immunity (serum), mL				●15		●15 q
Biomarker RNAseq blood sample (PAXgene tubes, whole blood), mL r				●2.5		●2.5

In case of signs and symptoms: Symptoms of Infection with Coronavirus-19 (SIC), including highest body temperature over the last 24 hours measured by the participant s (ePROs to be completed by the participant in the eCOA)	----- Daily -----					● t
In case of no signs or symptoms: (Suspected) COVID-19 surveillance (symptom check)	----- At least twice a week -----					●
Risk factor assessment u			●			
Vital signs v		●				●
Targeted physical examination		●				●
Pulse oximetry by site staff		●				●
Pulse oximetry by the participant (ePRO to be completed by the participant in the eCOA) w	● b	----- 3 times a day -----				
Medical history (including recent flu or pneumococcal vaccination) and description of COVID-19 episode (collected by interview with the participant)			●			●
MRU questionnaire (collected by interview with the participant) x			●			●
Capture medical information from medical visits for COVID-19 or COVID-19 complications (MA-COV form) y	----- Continuous -----					
Concomitant therapies associated with COVID-19	----- Continuous -----					
Study-site personnel to contact participant	----- Weekly or more frequently -----					

- a. The visit at COVID-19 Day 3-5 should be scheduled 2 to 4 days after symptoms onset/positive RT-PCR test from outside the study.
- b. Only applicable for participants that meet the prespecified criteria for suspected COVID-19 (Section 8.1.1) on COVID-19 Day 1-2 and COVID-19 Day 3-5 or who have a positive test result for SARS-CoV-2 on COVID-19 Days 1-2 or 3-5 visits.
- c. Participants should be encouraged by the site to collect nasal swabs and saliva samples as indicated in the Schedule of Activities. If the participant is unable or unwilling to collect all samples as requested, the participant should still complete the other COVID-19 assessments, including the visit at COVID-19 Day 29.
- d. As soon as it is confirmed that both nasal swabs (collected on COVID-19 Day 1-2 and COVID-19 Day 3-5) are negative for SARS-CoV-2, the participant will not undertake any further COVID-19 procedures and will fall back to the default Schedule of Activities, until the end of the study/early withdrawal.
- e. Participants should undertake the COVID-19 procedures until 14 days after symptom onset (COVID-19 Day 15) or until resolution of the COVID-19 episode, whichever comes last. Resolution of a COVID-19 episode is defined as having 2 consecutive SARS-CoV-2 negative nasal swabs and 2 consecutive days with no COVID-19-related signs or symptoms. Once past COVID-19 Day 15, participants should stop the collection of nasal swabs and saliva samples as soon as 2 consecutive nasal samples are SARS-CoV-2 negative, but (if still symptomatic at that time) should continue completing the ePROs (including SIC, body temperature, and pulse oximetry) in the eCOA until 2 consecutive days with no COVID-19-related signs or symptoms (Section 8.1.1).
- f. Only applicable for participants that have at least 1 SARS-CoV-2 positive nasal swab collected on COVID-19 Day 1-2 or Day 3-5. COVID-19 Day 29 should still be performed even if the nasal swabs results are still pending.
- g. The visit on COVID-19 Day 29 can be combined with a regular study visit if within the applicable visit windows.
- h. The COVID-19 Day 1-2 nasal swab can be collected at the study site (or hospital or other location, if needed), if preferred by the participant.
- i. All COVID-19 Day 3-5 and Day 29 assessments may be performed by a trained HCP at the participant's home, if allowed per local and/or institutional regulations.
- j. If a participant has a positive test result for SARS-CoV-2 infection and/or depending on the medical status of the participant, the participant may be requested to remain at home and not visit the study site. If necessary, study-site personnel or a trained HCP will visit the participant at home (or at the hospital or other location, if needed), if allowed by local regulations. Under these circumstances, the participant will be contacted by the site at least once per week and the participant's medical care provider will be notified.
- k. In case of COVID-19 like symptoms, based on the information collected through the SIC, the site will reach out to the participant at the latest on COVID-19 Day 2 (the day after the day of symptom onset) to assess whether the reported signs and symptoms qualify as a suspected COVID-19 episode using prespecified criteria

(Section 8.1.1). As several of the prespecified criteria for suspected COVID-19 overlap with vaccine-related reactogenicity, investigators' clinical judgement is required to exclude vaccine-related events. In case the participant would actively reach out to the site already on COVID-19 Day 1, the site should already make a first assessment on COVID-19 Day 1 to check whether the reported signs and symptoms qualify as a suspected COVID-19 episode using prespecified criteria (Section 8.1.1).

1. In case of COVID-19 like symptoms, the site will interview the participant to assess whether the reported signs and symptoms still qualify as a suspected COVID-19 episode using prespecified criteria (Section 8.1.1).
- m. A nasal swab should be collected from the participant at home (using available material for home swabs provided by the study staff) as soon as the prespecified criteria for suspected COVID-19 are met and, in case of COVID-19 like symptoms, preferably on the day of symptom onset or the day thereafter (COVID-19 Day 1-2). The sample collected on COVID-19 Day 1-2 should be transferred to the study site, as arranged by the study site, as soon as possible after collection, preferably within 24 hours. Nasal swabs should also be collected once every 2 days until 14 days after symptoms onset (COVID-19 Day 15) or until resolution of the COVID-19 episode, whichever comes last. These samples should be transferred to the study site, as arranged by the study site, within 3 days after collection. Details are provided in the laboratory manual. If the participant requires assistance, a trained HCP can help the participant to collect the nasal swabs. If 2 consecutive nasal swabs negative for SARS-CoV-2 are not available due to operational reasons (eg, delays in results availability), participants may cease collection of nasal swabs and saliva samples after COVID-19 Day 29, provided they have 2 consecutive days with no COVID-19-related signs and symptoms. In these cases, participants may be asked to resume sample collection if nasal sample results—once available—do not present with 2 consecutive negative swabs for SARS-CoV-2.
- n. The nasal swab should be collected and pulse oximetry should be started as soon as possible after it has been confirmed that the prespecified criteria for suspected COVID-19 (Section 8.1.1) are met.
- o. For participants with suspected COVID-19, confirmation of SARS-CoV-2 infection by RT-PCR or other molecular diagnostic test performed at a central laboratory will be used for the analysis of the case definition. All nasal swabs will also be tested by a local laboratory for case management.
- p. Saliva samples should be collected from the participant (using recipients provided by the study staff). The samples should be transferred to the study site, as arranged by the study site, within 3 days after collection. Details are provided in the laboratory manual. If the participant requires assistance, a trained HCP can help the participant to collect the saliva samples.
- q. Blood sample for humoral immunity also includes sample for sero-confirmation of SARS-CoV-2 infection (antibody).
- r. Blood sample for exploration of biomarkers correlating with SARS-CoV-2 infection and COVID-19 severity.
- s. Participants should complete the (suspected) COVID-19 surveillance (symptom check). In case of COVID-19 like signs and symptoms, participants should be encouraged by the site to complete the SIC (Appendix 6) daily, preferably in the evening around the same time each day, starting on the first day they experience symptoms. Sites should remind the participant to complete the SIC, unless special circumstances occur such as hospitalization or ventilation, in which case the reason for not completing the SIC should be recorded by site staff in the clinical database. If signs and symptoms are still ongoing on **COVID-19 Day 3-5**, collection of SIC will be continued until AT LEAST 14 days after onset UNLESS both **COVID-19 Day 1-2** and **COVID-19 Day 3-5** are both negative. If either of the swabs is positive or the result is unknown AND the participant is beyond 14 days after onset of symptoms, the SIC can be stopped after 2 days without signs and symptoms. If a participant is unable to complete the eCOA, a study staff member or the participant's caregiver can collect information on the participant's behalf as detailed in Section 8.1.2. Participant should measure body temperature daily (oral route preferred, or in accordance with the local standard of care) and record the highest temperature in the last 24 hours.
- t. If the participant does not have symptoms at that time, he/she will only need to complete the (suspected) COVID-19 surveillance (symptom check).
- u. If allowed by local regulations and if the participant consents, he/she will be interviewed on characteristics related to their current work situation, living situation, and community interactions (See Appendix 12). These data will be used for risk factor analysis.
- v. Includes measurement of vital signs (preferably supine systolic and diastolic blood pressure, heart rate, and respiratory rate [after at least 5 minutes rest] and body temperature). It is recommended that vital signs are measured before collection of nasal swabs and blood draws.

- w. In case of COVID-19 like symptoms, the participant will be asked to measure blood oxygen saturation and pulse rate at home 3 times a day (preferably in the morning, at lunch time, and in the evening). The results will be recorded by the participant in the eCOA.
- x. Data collected as part of the MRU will be recorded in the eCRF.
- y. The MA-COV form ([Appendix 8](#)) will be provided to the participant at the vaccination visit and should be completed by the medical care provider or the study site personnel during medical visits for COVID-19 or COVID-19 complications.

Upon closure of the COVID-19 episode and procedures, all participants will fall back to the default Schedule of Activities, until the end of the study/early withdrawal. If the participant experiences new signs or symptoms suggesting possible COVID-19 at a later point in time, the participant would re-start the COVID-19 procedures from COVID-19 Day 1 onwards.

COVID-19 = coronavirus disease-2019; eCOA = electronic clinical outcome assessment; eCRF = electronic case report form; ePRO = electronic patient-reported outcome; MA-COV = medically-attended COVID-19; MRU = medical resource utilization; SARS-CoV-2 = severe acute respiratory syndrome coronavirus-2; SIC = Symptoms of Infection with Coronavirus-19.

